Phase II: 20 additional subjects with post-COVID-19 infection coming to the COVID-19 clinic at Baylor College of Medicine for treatment of complications (i.e., hospital acquired weakness due to neuromyopathy). Patients will begin the study after being diagnosed with neuromyopathy due to prolonged hospitalization for COVID-19. This will be performed by a critical care and pulmonary specialist at the BCM COVID-19 Clinic. The entire cohort will receive daily electrical stimulation in lower extremity (e.g. Gastrocnemius, tibial anterior muscle) up to 1 hour to recover from Neuromyopathy complications and prolonged hospital stay. The patients will take the device home up to 4 weeks and will be screened once a week at the COVID-19 clinic for neuromuscular evaluation.

Inclusion Criteria:

Age: Adults age 18 years or older Disease status: COVID-19 test positive Critically ill requiring care in the hospital.

Patients must have been previously hospitalized due to COVID-19 infection and diagnosed with hospital acquired weakness by pulmonary care specialists. Patients will have to be alert and conscious to sign the consent form.

Exclusion Criteria:

Subject has a demand-type cardiac pacemaker, implanted defibrillator or other implanted electronic device Active wound infection Below the knee amputations Based on the clinicians decision whether the patient is eligible for the study.

F2. Procedure

Phase I:

Aim1 (to understand mechanism of action): Examine immediate benefit of lower extremity EE to improve venous return flow, tissue oxygenation, and muscle activation (short term benefit). In this study, we will recruit a convenient sample of 20 hospital patients diagnosed with COVID-19 (short-term benefit).

Optional: Subjects will be assessed using Doppler ultrasound and near infrared imaging (Kent Imaging System) at pre-, 30min, 60min, and 30min post-treatment (after stopping of EE device). Lower extremity muscle activation will be assessed by using sEMG (electromyography).

Patients will begin the study after being admitted to the hospital no more than 48 hours.

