The protocol will consist of 4 weeks of lower-extremity electrical stimulation. Opposite to our initial study, this modality will consist of home-based therapy, meaning that the patient will take the device home and attend the clinic once a week for screening and assessment of therapy.

The protocol will be performed as the following description: This trial will have 20 patients divided in two groups. Group 1 (intervention, n=10): Will receive an active Tennant Biomodulator Group 2 (control, n=10): Will receive an inactive Tennant Biomodulator This study will consist of 5 visits total and one phone interview 12 weeks after baseline for both groups. The patient will be compensated \$50 per visit (total \$250), with free parking. Payment will only be available for subjects who participate in Part II.

During the first and last visit, the research staff will turn the Tennant Biomodulator PRO® on for one hour and measure any changes in muscle strength, endurance, and blood flow after the therapy. Once the first visit is over, the patient will take the Tennat Biomodulator® home and will be instructed to turn it on for one hour every day for four weeks.

The visits in-between will be performed in the following order: 1) Questionnaires (pain, weakness, sleep, quality of life, frailty, depression, life and space, beck anxiety scale, Katz-daily living) 2) Musculoskeletal assessments (non-invasive surface electromyography, vibration perception threshold) 3) Vascular assessments (non-invasive Near infra-red spectroscopy)

After 4 weeks, the patients will turn back the device to the research staff.

The supervision of this study will be by pulmonary care specialists, and the location will be at the recently open COVID-19 clinic at Baylor College of Medicine.

Section G: Sample Size/Data Analysis

G1. Sample Size

How many subjects (or specimens, or charts) will be used in this study?

Local: 40 Worldwide: 40

Please indicate why you chose the sample size proposed:

Sample size is convenient and selected based on available resources to demonstrate feasibility and the proof of concept effectiveness of EE therapy for COVID-19 patients admitted to ICU and post-ICU. We plan to recruit 40 eligible subjects.

G2. Data Analysis

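### Phase II is described both as a single cohort in which everyone is stimulated and as 10 active v 10 inactive, with no random allocation stated and no between-group contrast named for the 4-week home phase

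*Protocol*

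**What the plan says.** **Protocol F1 (Design).** Phase II has its own sample: "Phase II: 20 additional subjects with post-COVID-19 infection coming to the COVID-19 clinic at Baylor College of Medicine". Of these patients F1 says: "The entire cohort will receive daily electrical stimulation in lower extremity (e.g. Gastrocnemius, tibial anterior muscle) up to 1 hour to recover from Neuromyopathy". The form's prompt asks about group assignment, placebo and control subjects; the Phase II answer mentions none of them.

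**Protocol F2 (Procedure, Phase II).** The opening line again makes no distinction between patients: "The protocol will consist of 4 weeks of lower-extremity electrical stimulation". The next paragraph sets out two groups: "This trial will have 20 patients divided in two groups", then "Group 1 (intervention, n=10): Will receive an active Tennant Biomodulator Group 2 (control, n=10): Will receive an inactive Tennant Biomodulator". How patients reach a group is not stated. On the clinic sessions it says: "During the first and last visit, the research staff will turn the Tennant Biomodulator PRO® on for one hour and measure any changes". The home-use instruction that follows also has the patient switch the device on daily, with no distinction by group. Inactive is not defined.

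**Analysis text.** G2 lists baseline and discharge as the scheduled time points and expects the measurements to change from baseline to the end of the intervention. It does not name active v inactive. Section I, under potential benefits, refers to mixed models or GEE for an intervention effect, without naming the contrast. The SAP fits group (CG, IG) by time at baseline, 3 days and 9 days, and its title concerns critically ill patients.

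**The concern.** Phase II is meant to show recovery from neuromyopathy in patients who have left hospital. The protocol attributes that weakness largely to the hospital course: immobilisation, paralytics and glucocorticoids. Some improvement over 4 weeks without the device is therefore plausible, although the documents give no rate for it.

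Whether Phase II can say anything about effectiveness then depends on whether it has a control group, and the protocol answers this both ways. With one cohort, any natural recovery is counted as device benefit. With two groups, recovery is common to both arms and drops out of the difference, provided the groups are comparable and the control device delivers nothing. The protocol does not secure either condition, because the allocation method and the meaning of inactive are both left open.

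**Working it through.** **1. The plan's own counts.** F2: 10 + 10 = 20, which matches the 20 Phase II subjects in F1. With the 20 in Phase I, 20 + 20 = 40, which matches G1. So F1 and F2 describe the same 20 people, and the conflict cannot be explained as two separate samples. G1 calls the sample size one of convenience and gives no power figure to reproduce.

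**2. Does any other section decide between F1 and F2?**

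- F2's opening line fits F1; its next paragraph contradicts F1.
- G2 describes change from baseline, which fits a single cohort. Its ANOVAs compare risk-factor groups and men with women, not devices.
- Section I's intervention effect fits either design.
- The SAP has two groups, but its time points (days 3 and 9) and population do not fit a 4-week home phase with weekly clinic visits.

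None of these decides it.

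**3. Consequence if F1 is followed (illustration).** Inputs: n = 20 (F1) and two-sided alpha 0.05 (G2). Assumptions: no device effect; natural recovery of d SDs of the change score; a one-sample (paired) t-test on the change. The plan does not name that test; it stands in for G2's change-from-baseline reasoning.

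Probability of significance in the direction of benefit = P(T > 2.093), where T is noncentral t with 19 df and noncentrality d × √20 = d × 4.472.

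| Assumed recovery d | Noncentrality | Probability |
|---|---|---|
| 0.3 | 1.342 | about 25% |
| 0.5 | 2.236 | about 56% |
| 0.8 | 3.578 | about 92% |
| 1.0 | 4.472 | about 99% |

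The nominal rate in that direction is 2.5%. A randomised active v inactive comparison would hold the two-sided error at 5% per test whatever the value of d. This is per test only, since Section I names three primary outcomes.

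**4. Consequence if F2 is followed and controls had live sessions at the first and last visits (illustration).** Home use is 7 × 4 = 28 sessions and the clinic adds 2, so about 30. Controls would receive 2/30, about 7%, of the active exposure. Assume the effect is proportional to sessions. With 10 v 10, a t-test at two-sided 0.05 has 80% power for a standardised difference of 1.32. Dilution gives 1.32 × (1 − 0.067) = about 1.24, with power of about 74%. For a true difference of 1.0, power falls from about 56% to about 51%. The 4-week contrast largely survives. What would be lost is the immediate before-and-after-session contrast at those two visits, because both groups would have had the same session.

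**5. If F2 is followed with a sham that delivers nothing when on.** Natural recovery is separable in principle.

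**The case against.** The strongest reply is that F2 is plainly the operative text. It comes later, is more specific, and is introduced as the way the protocol will be performed. The F1 Phase II sentence nearly repeats the Phase I sentence and may simply have been carried over. On that view Phase II is controlled and the figures in step 3 describe a trial nobody intends to run. This carries weight: F2 may well be the intended design, and the 25% to 99% range applies only if F1 is followed. It does not remove the contradiction. F2's own opening line and G2's change-from-baseline language both fit F1, and staff working from the protocol should not have to infer whether there is a control group.

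It is also fair to object that the recovery sizes are not sourced, and that the plan names residualised change scores, ANOVA and mixed models or GEE, not a paired t-test. Both points stand. The figures show direction and rough scale only.

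Three stronger readings are tempting, and the documents do not support them:

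- *Controls are stimulated at the first and last visits.* The clinic sentence makes no exception for controls, but the same switching-on language covers home use, where it would make inactive meaningless. It fits switching on a unit that delivers nothing. This is an ambiguity, not evidence of live stimulation.
- *Staff will steer active devices to patients likely to recover.* The text says only that patients are divided. A missing allocation method leaves room for selection but does not show it. The SAP title does say randomised; since that SAP does not describe Phase II, it neither supplies the method nor proves its absence.
- *The causes of weakness have ended, so recovery is certain.* The protocol also lists inflammation, perfusion and hyperglycaemia, and does not say that these, or steroids, have stopped by Phase II.

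**Conclusion.** The concern holds as an unresolved contradiction over whether Phase II has a control group, together with an unstated allocation method and no named between-group contrast for the 4-week phase. The contradiction itself rests on the text alone and needs no assumption.

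Its size depends on which version is followed. Under F1, a device with no effect would look beneficial in about 25% to 99% of trials, for assumed recovery of 0.3 to 1.0 SD of the change score and a pre-post t-test with n = 20. Under F2 with a true sham and random allocation, natural recovery does not bias the comparison. The undefined inactive device is a separate and smaller matter. Even if controls were live at two visits, the expected loss is mainly the immediate post-session contrast, with 4-week power falling from about 80% to about 74% under proportional effect.

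**What to change.** Reconcile F1 and F2 into one Phase II design statement. The sponsor has to say which design is meant.

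*If two groups are intended:*

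- Remove the all-stimulated sentence from F1 and align F2's opening line.
- Replace the statement that patients are divided with random allocation 1:1 from a concealed list. Concealment matters because an open list would not prevent selection.
- State what an inactive device delivers when switched on, both in clinic and at home.
- In G2 or the SAP, base the Phase II effectiveness conclusion on the active-minus-inactive difference at 4 weeks.

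*If a single cohort is intended:* remove the two-group text from F2, and limit Phase II to feasibility and descriptive change, with no effectiveness conclusion.

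The first option costs protocol and SAP wording plus a concealed 1:1 list. It needs no extra patients, visits or devices, since 10 inactive units are already planned. The second costs only wording, but gives up any claim of effectiveness from Phase II.

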The risk to participants of this study is considered to be minimal in a controlled environment with an attendant present. This research routine will not place subjects at higher risk than normal activities of daily living, and no more risk of harm or discomfort is associated with these tests than the discomfort normally incurred while performing normal muscle stretching. Subjects will be allowed rest time between trials as needed. The EMG device will detect level of fatigue and based on that we will determine the length of the sessions.

The devices and technology is completely non-invasive, safe, non-toxic and non-ionizing. The potential risks to subject are minimal. However, like any battery powered systems, there is a minimum risk of sensor malfunctioning. In addition, the study devices are not waterproof, and although they use a low powered battery (similar to a cellphone battery), in order to avoid any risk of shock the monitor should not be submerged or saturated with fluids during operations or cleaning. It does not emit any radiation to the human body, and does not offer any significant risk to the subject.

Subjects may experience mild discomfort from the sensor on their legs. We will inform the subject to please notify the investigators if the sensor is uncomfortable.

All information we will collect about the subject will be stored in a secure location and coded in a way to maintain confidentiality. Only study personnel will have access to their records. Data collected during the study may be published and made publicly available. Data may also be shared with other research groups. However, data that could in any way identify them will not be made public or shared.

Some of potential risks of using TENS therapy could be: * Skin related discomfort, such as tingling * Skin reaction to adhesive patch.

If the tingling sensation is too intense for the participant, they have the ability to reduce the intensity for their best level of comfort.

H2. Data and safety monitoring plan

Do the study activities impart greater than minimal risk to subjects?
No

H3. Coordination of information among sites for multi-site research

Is the BCM Principal Investigator acting as the SPONSOR-INVESTIGATOR for this multi-site research?
No or Not Applicable

Is BCM the COORDINATING CENTER for this multi-site research?
No or Not Applicable

Section I: Potential Benefits

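### Phase II provides no masking of measurer or patient, so active-inactive differences on effort-based and self-reported outcomes may mix expectation with device effect

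*Protocol*

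**What the plan says.** Protocol F2 (Procedure, Phase II) splits 20 patients into an active arm of 10 and a control arm: "Group 2 (control, n=10): Will receive an inactive Tennant Biomodulator". At the first and last visits "the research staff will turn the Tennant Biomodulator PRO® on for one hour and measure any changes in muscle strength, endurance, and blood flow" once the hour is over. Between visits the patient "will be instructed to turn it on for one hour every day for four weeks". The in-between visits cover nine questionnaire domains, sEMG, vibration perception threshold (VPT) and near-infrared spectroscopy; no one is named as the measurer.

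H1 lists "Skin related discomfort, such as tingling" among the possible risks and adds: "If the tingling sensation is too intense for the participant, they have the ability to reduce the intensity for their best level of comfort".

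Section I names VPT, sEMG and tissue oxygenation as primary outcomes, without separating the phases, and plans mixed models or GEE to test the intervention effect on each outcome. Dynamometer weakness is secondary.

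Neither document mentions blinding, a sham output, coded devices, a separate assessor or a check on what patients believe. F1 says that everyone in Phase II receives stimulation, which does not fit the inactive control in F2.

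**The concern.** An inactive device is there mainly to make expectation equal in the two arms. That works only if patients cannot readily tell which device they have and measurers do not know. The plan protects neither condition.

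VPT depends on the patient's response, strength and endurance depend on effort, and the questionnaires are self-report. G2 also records the direction the investigators expect: parameters should improve, and EMG voltages should rise. In the protocol's only controlled comparison, a modest expectation or assessor effect would be hard to tell from benefit, and it would more plausibly favour the device than not. A misleading signal would carry into the planning of the next trial.

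**Working it through.** **1. Who could know the arm, outcome by outcome (F2, Phase II)**

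| Outcome | Visit | Measurer | Dependence on the patient |
|---|---|---|---|
| Strength, endurance | First and last | Same staff group as switches the device on | Effort |
| Blood flow | First and last | Same staff group | Little |
| VPT | In-between | Not named | Patient's response |
| Questionnaires | In-between | Not named | Self-report |
| sEMG | In-between | Not named | Depends on whether the contraction is voluntary; not stated |
| Tissue oxygenation | In-between | Not named | Little; read by instrument |

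The evidence for an unmasked assessor is therefore confined to the first- and last-visit measures. For VPT and the questionnaires the route is the patient's own inference from sensation.

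**2. Scale**

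There is no figure in the plan to reproduce. G1 calls the sample one of convenience and gives no effect size, SD or power.

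- From the documents: 10 per arm (F2); two-sided 0.05 (G2).
- Assumed: no true device effect; an expectation effect of *b* SD when the arm is fully known; a between-arm difference *g* in the share of patients who believe their device is active. The resulting shift is *d = b × g*.
- Test: two-sample t-test, as a stand-in for the planned mixed models or GEE. Degrees of freedom 18, critical value 2.101, noncentrality = *d* × √(10/2) = 2.236 *d*. The rejection rate is the probability that the noncentral t exceeds 2.101 in absolute value.

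| *b* | *g* = 1: shift, noncentrality | Rejection | *g* = 0.5: shift, noncentrality | Rejection |
|---|---|---|---|---|
| 0.3 | 0.30, 0.671 | 9.7% | 0.15, 0.335 | 6.2% |
| 0.5 | 0.50, 1.118 | 18.5% | 0.25, 0.559 | 8.3% |
| 0.8 | 0.80, 1.789 | 39.5% | 0.40, 0.894 | 13.5% |

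With *g* = 0 the rate is 5.0%.

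**3. Could the data reveal it?**

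The half-width of a 95% interval for the difference is 2.101 × √(2/10) = 0.94 SD. Every shift in the table is smaller, so the result itself would not show it. A larger sample would narrow the interval but leave the shift in place.

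**The case against.** The strongest reply is that silence is not evidence of unmasking, and much of it stands.

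- A reader might infer that one person switches on and measures, and sees whether the unit works. F2 does not say so. Research staff is a collective term, and no text says that activity is visible. What stands is that nothing requires separate people or an unaware measurer.
- A reader might infer that patients can certainly tell. H1 only says that tingling could occur. Phase II patients have diagnosed neuromyopathy and may turn the intensity down, so some active users may feel little. The documents do not describe what the inactive unit does. Likely able to infer is as far as the text goes.
- A reader might extend the dual role to VPT and the questionnaires. The quoted sentence does not cover them.
- A reader might take the no answer to placebo control (O1) as proof that there is no sham. That question sits in the drug section and does not settle it.
- The consent pages are not in our copy, so what patients are already told about sensation cannot be judged.
- This is a pilot of convenience size. But G1 aims at proof-of-concept effectiveness and Section I tests the intervention effect on each outcome, so the interpretation of a difference still matters.

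The SAP does not help either way. It compares two groups at baseline, 3 days and 9 days, which does not match Phase II's weekly visits.

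**Conclusion.** The concern holds in a limited form and should be acted on. As written, Phase II leaves the active-inactive difference on VPT, strength, endurance and questionnaires open to expectation. For strength, endurance and blood flow at the first and last visits it is also open to an unmasked assessor. Tissue oxygenation is the least exposed primary outcome, although its operator is not stated to be masked.

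The size is illustrative. The false-positive rate rises from 5% to between 9.7% and 39.5% if the whole assumed shift of 0.3 to 0.8 SD operates, and to between 6.2% and 13.5% if half does. The shift, its favourable direction and the degree of unmasking are all assumptions. It would be wrong to read the higher figures as the trial's actual error rate.

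The point also presumes that the inactive control in F2 is what is run, which F1 leaves unclear.

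**What to change.** With existing staff:

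1. Number the devices. Whoever sets up and switches on the device takes no outcome measurement at any visit. The measurer enters after the device is off and removed, and does not hold the allocation list. Name the measurer role for the in-between visits too.
2. Process tissue-oxygen images and sEMG without knowledge of group.
3. Use the same neutral wording about sensation for both arms.
4. Ask patients to guess their arm after the first session and again at week 4, and ask the measurer at week 4. Report the guesses descriptively, not as a decision rule. A week-4 guess alone partly reflects perceived benefit, and with 10 patients in an arm, 5 of 10 correct has an exact 95% interval of about 19% to 81%.
5. State that differences on self-reported and effort-based outcomes may include expectation, and give interpretive weight to tissue oxygenation.
6. Reconcile F1's statement that the whole Phase II cohort is stimulated with F2's inactive control. Also clarify whether H1's use of EMG fatigue to set session length refers to stimulation sessions. If it does, that reading has to be kept apart from the masked measurer's role.

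The cost is a role split, one sentence of patient information and a few short questions, with slightly more scheduling per visit. Patient blinding may remain imperfect.
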